### **Sample size justification**

The sample size calculation is based on detecting a weak positive correlation coefficient between variables ( $r=0.2$ ). Assuming this, a sample size of at least  $n=194$  will be required to have 80% power ( $\beta=0.2$ ) at  $\alpha=0.05$  significance.

There are between 330 and 350 women eligible to complete this questionnaire from Part 1 of this study. We anticipate that asking 350 women to take part will result in responses from  $n=210$  women, assuming a 60% response rate.

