#### Psychological, cognitive and behavioural effects of breast cancer risk communication

Risk prediction models have been found to support informed choices in women identified via FHRPCs as being at high risk of developing breast cancer in relation to aiding difficult decisions around risk reducing surgery (Evans, Baildam, et al., 2009; Evans, Laloo, et al., 2009). One of the largest research

studies to explore the use of risk prediction in a population-level breast screening programme was conducted in Greater Manchester with over 56,000 women (Predicting Risk of Breast Cancer at Screening, PROCAS; Evans et al., 2016). One of the main reasons for the study was that only around 1 in 6 women in the population who would receive a high-risk estimate (and thus was eligible to receive more frequent screening or discuss preventative measures) have been identified. One might think that because this figure is low, women are not interested in knowing their breast cancer risk. However, a key finding from Evans and colleagues (2015) was that 96% of women (excluding those who received an 'average' risk estimate; 2-4.99%) wanted to receive their risk upon receipt of a risk appointment invite. Similarly, 70% opted to have a face to face appointment to discuss their risk. Interestingly, those who received high risk estimates were more likely to attend a review appointment (74%) compared to women who received moderate (73%) or low risk estimates (55%).

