#### **Storage of recalculated risks:**

Recalculated risk and risk information, i.e. SNP data and MD data are classed as clinical results and will be stored in patient FHRPC notes at the Nightingale Centre, stored on clinic computers on MFT's secure computer system. Images to calculate mammographic density will be used by UoM staff which honorary contracts with MFT. These images will be anonymised for the purpose of this analysis and will then be de-anonymised when being fed back to the patient. This is so UoM clinical staff with honorary contracts at MFT do not see any patient identifiable data. Images will not be retained on

UoM systems. Written clinic notes for women who consent to a consultation will be stored at the Nightingale Centre in the FHRPC in secure cabinets.

An anonymised database of all FH-Risk women's previous and updated breast cancer risk estimates will be stored on the MFT secure computer system. Only the clinical care team will be able to link this data back to women via a unique participant number.

A second anonymised database of women's previous and updated breast cancer risk estimates (who are still in follow up) will be stored on the MFT secure computer system. Only the clinical care team will be able to link this data back to women via a unique participant number.

Anonymised databases will be retained for at least 10 years after the study in accordance with UoM's retention policy.

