## Analysis

Data will be analysed using correlational analysis and regression modelling. For example, correlational analysis will be used to assess the relationship between objective risk and women's subjective understanding of their risk, as well as the correlation between objective and subjective risk and cancer worry. Regression modelling will be used to explore which risk factors women attribute to their risk. Descriptive statistics will also be used for the satisfaction measure.

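### Part 4 analyses only the women who return the questionnaire; a respondent comparison and a weighted sensitivity analysis are not planned, although Part 1 holds each mailed woman's first and updated risk

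*Combined protocol and SAP*

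**What the plan says.** - **Expected return.** Section 3.7, Sample size justification: "There are between 330 and 350 women eligible to complete this questionnaire from Part 1 of this study", and "We anticipate that asking 350 women to take part will result in responses from $n=210$ women, assuming a 60% response rate". The required number is 194, for a correlation of 0.2 with 80% power at the 0.05 level.
- **Who is mailed.** Section 3.7, Participants and recruitment: women who attended a Part 1 consultation about their updated risk, less those interviewed in Parts 2 and 3 and those who declined to hear about further studies.
- **What is already known about them.** Section 3.3, Storage of recalculated risks, says that all FH-Risk women's "previous and updated breast cancer risk estimates will be stored on the MFT secure computer system". The clinical care team can link these records by a unique participant number.
- **How returns are tracked.** Section 3.8 places that ID on each questionnaire before it is sent. Section 3.7, Procedure, has the clinical care team link returned questionnaires to Part 1 data, and the ID is removed about two weeks after receipt. One reminder letter is the only step against non-response.
- **How the data are analysed.** Section 3.7, Analysis, plans correlation and regression, and adds: "Descriptive statistics will also be used for the satisfaction measure". Neither that section nor any other plans a respondent comparison, weighting or a sensitivity analysis for non-return.

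**The concern.** Non-response enters the plan only as a factor that sets the mailing number. Several Part 4 objectives are nevertheless summaries over women given an update: whether they perceived a change, what they know about their risk, and how far subjective risk departs from objective risk. Satisfaction is to be described in the same way.

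A pooled summary from respondents differs systematically from the value for all mailed women when two things hold together: return varies with risk or direction of change, and so does the answer. For perceived change the second condition is close to certain, because the question is about the change itself. For knowledge, satisfaction and the objective-subjective gap it is plausible but assumed. An unadjusted correlation can also shift if respondents cover a narrower or wider range of risk than the mailed group. More returns at the same pattern of response would not reduce any of this.

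Most postal surveys know little about non-respondents. This one holds the most relevant covariates for all of them.

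**Working it through.** **1. The plan's own figures.** With Fisher's z, two-sided 0.05 and 80% power:

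n = ((1.960 + 0.842) / atanh(0.2))² + 3 = (2.802 / 0.2027)² + 3 = 193.97, so 194. This matches.

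Expected returns: 350 × 0.60 = 210 (power 83.1%) and 330 × 0.60 = 198 (power 80.8%). Women mailed but not analysed: 350 − 210 = 140, or 330 − 198 = 132.

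**2. Bias formula.** Let s_k be the share of mailed women in group k, r_k their return rate and y_k the proportion giving a certain answer. The mailed-group value is Σ s_k y_k. The respondent value is Σ s_k r_k y_k / Σ s_k r_k. If all r_k are equal, or all y_k are equal, the difference is 0.

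**3. Return differs between women whose category changed and those unchanged.** The mix comes from the pilot in section 1.2: 53/40/13 of 106, so 0.500 down, 0.377 same, 0.123 up. Assumed probability of reporting a change: 0.6, 0.2, 0.8. Overall return is held at 60%.

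Mailed-group value = 0.500×0.6 + 0.377×0.2 + 0.123×0.8 = 47.4%. SE = √(0.474×0.526/210) = 3.4 points.

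| Return, changed | Return, unchanged | Respondent value | Bias (points) |
|---|---|---|---|
| 60% | 60% | 47.4% | 0 |
| 65% | 51.75% | 49.6% | +2.3 |
| 70% | 43.5% | 51.9% | +4.6 |
| 50% | 76.5% | 42.8% | −4.6 |

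The unchanged rate is (0.60 − 0.623 × changed rate) / 0.377. In the third row the respondent mix is 0.583/0.274/0.143.

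**4. Return differs only between up and down.** With a gap of 10 to 30 points, the bias is 0.2 to 0.6 points for any perceived change. For a perceived increase (assumed 0.05, 0.10, 0.70 for down, same, up) it is 1 to 3 points.

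**5. Borrowing a gradient from the background section.** Section 1.2 reports review-appointment attendance of 74%, 73% and 55% for high, moderate and low risk in an earlier screening study. Assume half of the mailed women decreased, the others return at 73.5%, rates are scaled to 60% overall, and a fall is perceived by 60% of decreased and 10% of other women. The mailed-group value is 0.5×0.60 + 0.5×0.10 = 35.0%.

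| Where the decreases end | Rates before scaling | Decreased share of returns | Respondent value | Bias (points) |
|---|---|---|---|---|
| all in low | 55% v 73.5% | 42.8% | 31.4% | −3.6 |
| half low, half moderate | 64% v 73.5% | 46.5% | 33.3% | −1.7 |
| all in moderate | 73% v 73.5% | 49.8% | 34.9% | −0.1 |

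First row: 0.428×0.60 + 0.572×0.10 = 31.4%, SE = √(0.314×0.686/210) = 3.2 points. If 80% rather than 60% of decreased women perceive a fall, the first two biases are −5.0 and −2.4 points.

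**6. What weighting does.** In 4,000 simulated mailings of 350, with return of 70/45/65% (down/same/up) and the perception rates of step 3, the respondent-only figure averaged 51.3% against 47.3% for all mailed women. Weighting by direction-of-change group gave 47.3%, with an effective n of about 200 of 210. In the first row of step 5 the design effect is 1.021, so the effective n is 210/1.021, about 206.

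**The case against.** The strongest reply is that the documents contain no evidence that questionnaire return depends on risk. The 74/73/55% figures are attendance at an appointment, by absolute risk level, in a screening population. Every woman mailed in Part 4 has already opted in and attended a consultation, so the step those figures describe is behind her. That stands.

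A reader might still infer that the survey will under-represent women whose risk fell, with a bias as large as its sampling error. The documents do not support that. It requires giving every decreased woman the low-risk rate, whereas the pilot's definition of a decrease includes high to moderate, where 74% and 73% scarcely differ. Step 5 shows that this one choice moves the result from −3.6 to −0.1 points. The perception rates are invented as well. The pilot mix is not the Part 4 mix: it came from 106 women with SNP18 rather than SNP313, and up to 50 interviewees, sampled by direction of change, are removed before mailing.

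It is also fair that Part 4 is powered for a correlation and planned around correlation and regression. A regression that conditions on risk is not biased by selection on risk alone, and perceived change tabulated by actual direction of change is free of this component without weights. The concern is therefore confined to pooled descriptive results and unadjusted correlations.

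Finally, the free-text paragraph of section 3.7 shows that questionnaires had already gone out, so for early returns the ID may be gone. This limits an individual-level response model. It does not limit cell weighting: linked returns already carry Part 1 risk, and only counts of mailed women per cell are needed.

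**Conclusion.** The omission is real: 40% non-return is expected, returns alone are analysed, and data that could test and partly correct for selective return are held but not used. This is a low-cost improvement, not a demonstrated bias.

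The size cannot be derived from the documents. Under the assumptions shown, the bias in a perceived-change proportion lies between 0 and about 5 points, in either direction, against an SE of 3.2 to 3.4 points at n=210. It is 0 if return is unrelated to risk and direction of change, or if the answer is. No figure can be given for knowledge, satisfaction or the objective-subjective gap, and the size of any shift in the unadjusted correlations was not estimated. A reader might also suspect the sample size; 194 and 210 reproduce exactly and are unaffected.

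**What to change.** Add to section 3.7, Analysis:

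1. The clinical care team supplies counts of mailed and returned questionnaires by direction of category change, updated risk category, age band and follow-up status, using Part 1 data within existing consents.
2. Respondents and non-respondents are compared on these variables.
3. Perceived change is reported by actual direction of change.
4. Pooled descriptive results (perceived change, knowledge, satisfaction, objective-subjective gap) are reported unweighted and, as a sensitivity analysis, weighted to the mailed group. Cell weights suffice. A logistic response model may be used if return status can still be linked before the IDs are removed at about two weeks.

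Cost: some plan wording, one tabulation at the existing linkage step, and a few percent of effective sample size in the weighted figures (about 200 to 206 of 210 in the illustrations). Use of non-returners' Part 1 data needs a check against their consents; women who refused reuse of FH-Risk data were already excluded in section 3.2. Weighting will not correct for non-return driven by factors not held, such as worry or dissatisfaction, and the report should say so.

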### **Procedure**

Women will first be instructed to complete a copy of the consent form. They will receive two copies, one for their records and one for the study team. Following consent, women will be asked to complete the accompanying questionnaire. This should take no more than 10 minutes to complete. Once

complete women will be instructed to return their signed consent form and completed questionnaire in the pre-paid envelope provided. A reminder letter will be sent to women approximately 2 weeks after the first invite to gather additional questionnaires from those who may have forgotten to complete.

Once questionnaire responses have been received this information will be inputted onto a database and linked with women's data from Part 1 via their unique ID given to them in Part 1. This linkage will be carried out by members of the clinical care team at the hospital as they are the only ones who know how to link this data together. Once this data has been brought together their ID will be removed from the database and the dataset anonymised. This will happen approximately 2 weeks after receiving the questionnaire. All consent forms will be stored securely at UoM in a locked cabinet in a locked office.

**Free text response box procedure:** Since distributing questionnaires it has come to our attention that a minority of women are using the free text response box to pose questions to their clinician (who is the clinician on the study). Some of these questions require an answer and we would like to give these women the opportunity to speak with their clinician again as part of this study. We believe that we have a duty of care to provide this option. To do this, the researcher at the University who receives the completed questionnaires will provide women's study IDs and question response via a secure database to the research/clinical team at the hospital. As the hospital is able to link IDs to contact information, the clinician will identify these women and a member of the research team (on behalf of the clinician on this project) will contact those with questions and give them the opportunity to speak with their clinician further if they still want to. If women want a further conversation, an appointment will be arranged. A summary letter will be posted to women following their conversations, which will be copied to the GP if appropriate.

### Materials and methods

An invite letter, PIS, consent form and paper questionnaire (and pre-paid envelope) have been developed to distribute to women from Part 1 who attended a consultation and consented to hearing about future related research. Data will be gathered by a short questionnaire. Data from women's involvement in Part 1 and the FH-Risk studies will also be gathered from those who consented for their data to be used in future related research.

The questionnaire will include the following measures:

- A measure of comparative risk using the measure proposed by Weinstein (1999; *What does it mean to understand a risk? Evaluating risk comprehension*. *J Natl Cancer I Monogr* 1999; 25: 15-20).
- A measure of absolute risk using lifetime risk thresholds for breast cancer as defined by NICE clinical guidelines.
- A measure developed by the research team assessing for a perceived change in breast cancer risk.
- A measure developed by the research team assessing for women's knowledge about breast cancer risk factors.
- A measure of satisfaction regarding receiving an updated breast cancer risk estimate proposed by French et al (2004; *The psychological costs of inadequate cervical smear test results*. *Br J Cancer*. 2004;91:1887–1892).
- One item from the Leman cancer worry scale (1991) about developing breast cancer (*Psychological side effects of breast cancer screening*. *Health psychology*, 10(4), 259).
- *A free text response option to allow participants to identify anything important to them that the questionnaire may not have asked.*

## Analysis

Data will be analysed using correlational analysis and regression modelling. For example, correlational analysis will be used to assess the relationship between objective risk and women's subjective understanding of their risk, as well as the correlation between objective and subjective risk and cancer worry. Regression modelling will be used to explore which risk factors women attribute to their risk. Descriptive statistics will also be used for the satisfaction measure.

## 3.8 Data management for Part 4 (questionnaire study)

In accordance with data protection law, The University of Manchester is the Data Controller for this project. This means that we are responsible for making sure personal information is kept secure, confidential and used only in the way the participant has been told it will be used.

All data provided as part of the FH-Risk studies is stored on the secure NHS server on the hospital computer system by the study team. Notes from these studies are also stored in patient notes which are entered onto the clinic database based in the clinical secretary's office. A pseudonymised dataset is also stored at MFT and is linked to personal identifiable data via a study ID link. Only members of the research team can link this data to personal information. An anonymised database of all the data provided as part of the FH-Risk studies is also stored on the secure NHS server at the hospital, as well

as on secure servers at the University of Manchester. Women cannot be identified from this particular database.

Consent forms will be stored at the University of Manchester in the researchers locked office in a locked cabinet for up to 5 years following the end of the study and will then be destroyed. We will only retain participant contact details if they consent to being informed about future related research. If they do not consent to their contact details being retained we will destroy them once the findings have been written up for publication. Only authorised members of the research team will have access to this data. A database will be kept at Manchester University NHS Foundation Trust electronically of contact details for those who have taken part and who wish to be contacted again.

Completed paper questionnaires will be securely destroyed once data has been inputted electronically. This data will be pseudonymised using the participant ID number assigned to women when they received their updated breast cancer risk estimate in Part 1. This participant ID is only known to authorised members of the research team. This ID number will be inserted on each questionnaire before dispatch. Once data from their involvement in the present questionnaire study has been added to the data from the FH-Risk studies women's participant ID will be deleted from this database and the dataset anonymised, meaning we will not be able to identify any woman from this data. This will happen approximately 2 weeks after receiving the completed questionnaire.

Electronic material including, the pseudonymised and eventual anonymised database with the FH-Risk study data and questionnaire responses will be stored at the University of Manchester and as well as at Manchester University NHS Foundation Trust (Nightingale Centre, Wythenshawe Hospital) on secure, password protected computers. Electronic files containing 'personal identifiable information' will be deleted when they are no longer needed. Files containing 'personal identifiable information' will not be linked to women's questionnaire data.

The study team at The University of Manchester will have access to personal information and they will anonymise this as soon as possible. Names and any other identifying information will be removed and replaced with the ID number assigned to women in Part 1. The research team will have access to the key that links this ID number to women's personal information. Should women wish to opt out of us retaining this information, they can email the research team to request their removal.

## 4.0 CONSENT

All potential participants in each part of this study will receive notification of the study either via invite letter (Part 1, 2,3 & 4), email or telephone (Part 2 & 3). With this invite participants will receive a PIS. This sheet will contain all the relevant information needed about the study to make an informed decision as to whether to take part. All participants in each part of this study will have at least 24 hours to consider whether they would like to take part. In Part 1 women will fill in an expression of interest and consent to contact form and post it back to the study team, together with their consent form (during COVID19) if they would like to have a clinical appointment to discuss their risk. The clinical care team/authorised members of the study team will then contact the women to make this appointment. If clinical appointments are able to take place face to face (due to COVID19 face to face consultations may not be available) women can sign the consent form and expression of interest and consent to contact form at the appointment. For interviews taking place over the phone or zoom (Part 2 and 3), the researcher will read out each statement of the consent form and ask the participant if they agree. This will be audio recorded on an encrypted device and kept separate from study data. In part 4 (questionnaire study) women will receive a copy of the consent form and will be asked to complete this and post back in the pre-paid envelope provided with the completed questionnaire. Women in all parts of the study can contact the study team to ask questions at any time using the details on the PIS.

## 5.0 ETHICAL AND REGULATORY APPROVAL

The study will be conducted in full conformance with all relevant legal requirements and the principles of the Declaration of Helsinki, Good Clinical Practice (GCP) and the UK Policy Framework for Health and Social Care Research 2017.

### Research Ethics Committee (REC) and other Regulatory review & reports

The study will receive ethical review and approval from the necessary regulatory bodies. Before the start of the study, a favourable opinion will be sought from a NHS REC and Health Research Authority.

Amendments that require review by NHS REC will not be implemented until that review is in place and other mechanisms are in place to implement at site. All correspondence with the REC will be retained. The Chief Investigator will produce the annual report as required and notify the REC of the end of the study. An annual progress report (APR) will be submitted to the REC within 30 days of the anniversary date on which the favourable opinion was given, and annually until the study is declared ended. If the study is ended prematurely, the Chief Investigator will notify the REC, including reasons for the premature termination. A final report will be submitted with the results to the REC within one year after the end of the study.

Sponsor approval will be sought prior to the study commencing.

